#### **SCHEMA**

**TITLE:** Complementary and Alternative Medicine for Urological Symptoms

(CAMUS).

**DESIGN:** Randomized, double-blind, two arm trial with equal allocation to *Serenoa* 

Repens or placebo.

**POPULATION:** Males  $\geq$ 45 years old with peak urinary flow rate >4 ml/sec, voided volume

>125 ml, AUA symptom score >8 and <24.

**REGIMEN:** Participants will be randomized to one of the treatment arms:

• Serenoa Repens 320 mg once daily for 24 weeks followed by Serenoa Repens 640 mg once daily for 24 weeks followed by

Serenoa Repens 960 mg once daily for 24 weeks.

• Placebo for 72 weeks.

**DURATION:** Participants will continue on study treatment until they meet a protocol

defined reason for treatment discontinuation or complete 72 weeks of

follow-up at the assigned treatment.

**SAMPLE SIZE:** 350 participants randomized in a 1:1 allocation to *Serenoa Repens* or

placebo.

**PRIMARY** 

**OBJECTIVE:** To determine if *Serenoa Repens* reduces the AUA symptom score

compared to placebo over 72 weeks of treatment and is well tolerated.

## SECONDARY OBJECTIVES:

1. Determine if *Serenoa Repens* has a beneficial effect on subjective global assessment.

- 2. Assess the impact of *Serenoa Repens* on the following measures over time:
  - a. BPH Impact Index
  - b. Quality of Life item score from the IPSS
  - c. Nocturia item score from the IPSS
  - d. Peak uroflow
  - e. Post-void residual volume
  - f. Prostate Specific Antigen (PSA) level
  - g. Erectile and ejaculatory function
  - h. ICSmale Incontinence scale
  - i. Jenkins Sleep Dysfunction scale
  - j. NIH Chronic Prostatitis Symptom Index
- 3. Assess the impact of the assigned treatments on complete blood counts and basic blood chemistries.

#### 1.0 INTRODUCTION

#### 1.1 Study Rationale

The long-term efficacy and side effects of over-the-counter phytotherapies for men with lower urinary tract symptoms attributable to BPH are unknown, despite wide use of these agents by older men for maintaining "prostatic health." The overall goal of this study is to compare the efficacy of a widely available phytotherapy, extract of Serenoa Repens, against placebo in terms of impact on lower urinary tract symptoms. The phytotherapy selected for study has demonstrated short-term efficacy at relieving lower urinary tract symptoms with minimal side effects in a number of clinical trials. However, a recent NIDDK/NCCAM supported trial of Serenoa Repens at the 320 mg daily dose versus placebo did not demonstrate efficacy in terms of symptom reduction over 12 months of follow-up. As a result, this study is being conducted to compare higher-than-standard (double and triple) doses of this agent to determine its short-term effect on lower urinary tract symptoms and other parameters of BPH disease severity, and whether there is sufficient short-term efficacy and tolerability to merit testing for long-term efficacy in a long-term trial focused on the prevention of BPH progression. Because the study arm will use doses of this agent higher than generally used, participants will be monitored closely for toxicity/tolerability and have their doses slowly increased at 24-week intervals.

#### 1.2 Background

Benign prostatic hyperplasia (BPH) is a common cause of morbidity among older men in the United States and other developed countries. Although BPH is actually a histological process with an exact cause that is unknown, this condition confers its morbidity through potentially bothersome lower urinary tract symptoms (LUTS). In addition, men with BPH, and particularly those men with larger prostates as a result of BPH, are at increased risk for complications such as acute urinary retention and may progress to requiring surgical treatment for BPH. In fact, though the availability of effective medical therapy has reduced the need for transurethral resection of the prostate (TURP), the traditional surgical treatment for BPH, 132,000 TURPs were still performed in the U.S. in 2000,

according to the Centers for Disease Control's National Hospital Discharge Survey. Although there is debate about the working epidemiologic definition of symptomatic BPH, there is general agreement that the clinical manifestations of BPH are common. If an American Urological Association (AUA) symptom score of greater than 7 points (moderate to severe lower urinary tract symptoms) and a depressed peak uroflow rate (<15 mL/sec) are considered reflective of clinically important BPH, the condition affects 17% of men age 50-59, 27% of men age 60-69, and 35% of men age 70-79 (Jacobsen, 1995).

Men with bothersome lower urinary tract symptoms of BPH may choose from a spectrum of traditional medical treatments, including two classes of medications, alpha blockers and 5-alpha reductase inhibitors, minimally invasive therapies that generally use heat administered in different ways to damage or destroy prostate tissue, or a variety of surgical therapies, including TURP (AUA Practice Guidelines Committee, 2003). For men with symptoms that are not particularly bothersome at present, medical therapy may be a particularly attractive way to prevent the progression of symptoms, and even avoid future BPH complications, including the need for surgery.

The NIDDK sponsored Medical Treatment of Prostatic Symptoms (MTOPS) trial compared the ability of representatives of the two classes of medication for BPH, alone or in combination, to prevent BPH progression (McConnell, et al, 2003). In this trial, BPH progression was defined as a confirmed increase in AUA symptom score of 4 or more points, acute urinary retention, incontinence, urinary tract infection or urosepsis, or new renal insufficiency (in reality, almost all the progression events in the trial were in the first two categories). The drugs used were Finasteride, a 5-alpha reductase inhibitor, and doxazosin, an alpha-blocker. Finasteride blocks the conversion of testosterone to dihydrotestosterone, the major intraprostatic androgen, and reduces prostate size. Doxazosin blocks alpha-adrenergic receptors in the lower urinary tract, resulting in a reduction in smooth muscle tone in the prostate and bladder neck. Both of these drugs have been documented to be effective at reducing LUTS in men with a clinical diagnosis of BPH in previous trials (AUA Practice Guideline Committee, 2003). Combination

therapy with these two drugs over the long-term is an attractive concept, given their different mechanisms of action.

In the MTOPS trial, over a mean follow-up of 4.5 years, Finasteride and doxazosin were equally effective at reducing the rate of BPH progression, while combination therapy was significantly more effective than either agent alone (McConnell, 2003). The effectiveness profile of the two drugs was different. Doxazosin was more effective than Finasteride at reducing lower urinary tract symptoms, while Finasteride was more effective than doxazosin at reducing the rate of acute urinary retention and progression to surgery (although the latter was not part of the prespecified composite endpoint). Each drug had a side-effect profile similar to what would be expected from previous studies.

Another potentially promising class of medical therapies for the prevention of BPH progression is phytotherapy. Plant extracts are widely used in the United States (where they are sold as dietary supplements) and Europe (where they are often prescription drugs) by men with lower urinary tract symptoms. One of the best studied of these phytotherapies is extract of the fruit of *Serenoa Repens*, the Saw palmetto dwarf palm that grows in the Southeastern U.S.

Saw palmetto preparations of many varieties are widely used in the United States and Europe. The proposed mechanisms of action for Saw palmetto include 5-alpha reductase inhibition, intraprostatic androgen receptor blockage, and adrenergic receptor antagonism as well as an anti-inflammatory effect (Gerber, 2000). In a 2002 Cochrane meta-analysis of the effectiveness of Saw palmetto extracts for men with BPH, 21 randomized trials of 4 to 48 weeks duration were identified with 3193 subjects. Data from the trials indicated that compared to placebo, Saw palmetto reduced nocturia by 0.76 times per night (10 trials), increased the odds of self-rated improvement 1.76 fold (6 trials), and improved peak flow rates by 1.86 mL/sec (9 trials) (Wilt, 2002). Adverse effects were mild and infrequent. Methodological problems noted within the trials included lack of use of standardized symptom scores and short study durations. While trials have most

commonly used a dose of 160 mg twice daily, a comparative trial showed similar effectiveness with the more convenient dose of 320 mg once daily (Stepanov, 1999).

The STEP (Saw palmetto Treatment for Enlarged Prostates) study was a randomized, double-blind, placebo-controlled clinical trial of a saw palmetto extract for reducing BPH-related symptoms. Two hundred twenty-five men, aged at least 50 years old with baseline AUASI score ≥8, were randomized to saw palmetto 160 mg BID or a matching placebo (the saw palmetto extract used for this trial was manufactured by Indena and the placebo used was PEG-400). Participants were seen at quarterly intervals over a one-year follow-up period. The primary outcome was change in the AUASI score; secondary endpoints included changes in peak urine flow, post-void residual and detailed safety assessments (Bent, 2005).

Visit and medication adherence during the trial were excellent (97.5% of all study visits were kept and 91.6% of all study medications were returned by the participants). Analysis of the STEP data by mixed-effects models revealed no differences between study groups in changes in any of the primary or secondary endpoints. In particular, the between-group differences in the change scores (calculated as change in active-group scores minus change in placebo-group scores) were small and non-significant for the AUASI (0.04, 95% CI: -0.93 to 1.01), peak urine flow (0.43, 95% CI: -0.52 to 1.38), and post-void residual urine volume (-4.51, 95% CI: -24.44 to 15.42). The quality of the blinding appeared adequate as similar proportions of participants in the active and placebo study groups presumed they were on the active study medication at the end of the trial (40% vs. 46%, p = 0.38). No toxicity was observed with the saw palmetto extract in terms of serious adverse events, non-serious symptomatic adverse effects, or changes in laboratory parameters.

Extract of *Serenoa Repens* appears to have modest favorable effects on lower urinary tract symptoms and uroflow rates with few side effects. However, the trials documenting both the effectiveness and safety of this agent have many methodological problems, and the mechanisms of their clinical effect remain undefined. It is not clear if the results of

the STEP trial, which contradict the results of previous trials, reflect the play of chance or call into question the efficacy of *Serenoa Repens*, at least at the standard dose. Nonetheless, this agent is widely used, and if it is indeed effective at reducing lower urinary tract symptoms, might be preferred by many men based on the "natural therapy" appeal, its side-effect profile, and its cost, relative to the prescription medications for BPH.

The Saw palmetto product selected for use in CAMUS is produced by Madaus/Rotta-Pharm, and is an ethanol extract of Saw palmetto berries sold in Europe known as Prosta Urgenin. The same product is available in the United States, where it is sold under different brand names. The active ingredients are unknown, but the composition of this extract appears similar to other widely used Saw palmetto extracts, including the most intensively studied hexane extract. The extract method for the CAMUS product differs from the Saw palmetto product tested in the STEP trial, which was produced with a CO2 extraction process. The CAMUS Saw palmetto product is available in dark-colored gelcaps containing 320 mg of the extract, and the company will provide placebo gelcaps with an identical appearance.

#### 1.3 Study Design

CAMUS is a double-blind, randomized, multi-center trial to determine if *Serenoa Repens* reduces lower urinary tract symptoms compared to placebo. Participants will be randomized equally to one of two treatment arms: extract of *Serenoa Repens* 320 mg once daily for 24 weeks (one gelcap); followed by 640 mg daily for 24 weeks (two gelcaps) followed by 960 mg daily for 24 weeks (three gelcaps) or placebo. To maintain the double blind, all participants will take one gelcap daily for the first 24 weeks, two gelcaps daily during the second 24 weeks and 3 gelcaps daily during the next 24 weeks. Protocol treatment will be discontinued if the participant develops unacceptable toxicity, or meets one of the protocol-defined reasons for treatment discontinuation.

#### 2.0 OBJECTIVES

#### 2.1 Primary objective

The primary objective of CAMUS is to determine if Serenoa Repens reduces the AUA symptom score compared to placebo over 72 weeks of treatment and is well tolerated.

#### 2.2 Secondary Objectives

Secondary objectives of the study are to:

- 1. Determine if Serenoa Repens has a beneficial effect on subjective global assessment.
- 2. Assess the impact of Serenoa Repens on the following measures over time:
  - a. BPH Impact Index
  - b. Quality of Life item score from the IPSS
  - c. Nocturia item score from the IPSS
  - d. Peak uroflow
  - e. Post-void residual volume
  - f. Prostate Specific Antigen (PSA) level
  - g. Erectile and ejaculatory function
  - h. ICS*male* Incontinence scale
  - i. Jenkins Sleep Dysfunction scale
  - j. NIH Chronic Prostatitis Symptom Index
- 3. Assess the impact of the assigned treatments on complete blood counts and basic blood chemistries

#### 2.3 Subgroups

The primary and secondary outcome measures may vary by subgroups. Subgroup analyses will be conducted based on the following baseline measurements:

- 1. AUA Symptom Index and BPH Impact Index
- 2. Peak uroflow
- 3. Post-void residual volume

- 4. Prostate Specific Antigen (PSA) level
- 5. NIH Chronic Prostatitis Symptom Index

For each variable #1 - #4, three ordered categories will be created based on textiles of the respective distributions, and the relationship of the ordered categories to the outcome variables would be examined. For #5, the NIH-CPSI, the score will be dichotomized into two ordered categories, the threshold considered to indicate significant symptoms of chronic prostatitis.

Subgroup analyses of primary and secondary endpoints will be performed for subgroups defined by ethnicity and racial category.

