#### 3.2 Exclusion Criteria

Potential participants that meet any of the following exclusion criteria will be excluded from the full-scale trial:

- 1. Any prior invasive intervention for BPH.
- 2. Phytotherapy for BPH or a 5-alpha reductase inhibitor within 3 months.
- 3. Alpha blocker within one month.
- 4. Reported allergic reaction to Serenoa Repens.
- 5. Taken an oral alpha agonist, tricyclic antidepressants, and anticholinergic or cholinergic medication within 4 weeks of the first screening visit, with the following exception: topical anticholinergic eye drops used for glaucoma or inhaled anti-cholinergic used for COPD.
- 6. Taken an estrogen, androgen, or any drug producing androgen suppression, or anabolic steroids within 3 months.
- 7. Known clinically significant renal impairment (i.e., creatinine greater than 2.0 mg/dl).

- 8. ALT (SGPT), AST (SGOT) or GGT value greater than 3 times the upper limit of normal in the clinical center lab at SV1.0; confirmed on a second measurement.
- Prothrombin time greater than 3 seconds above the upper limit of normal, or more than 3 seconds above the control value in the clinical center at SV1.0; confirmed on a second measurement.
- 10. ECG reading at the clinical center at SV1.0 or SV2.0 suggesting active ischemia or recent myocardial infarction until appropriate consultation confirms the absence of an acute coronary syndrome.
- 11. PSA level greater than 10 ng/ml at the first screening visit.
- 12. Requires the daily use of a pad or device for incontinence, or ICS*male*IS score >14 at screening.
- 13. Unstable medical condition within the past 3 months.
- 14. History or current evidence of carcinoma of the prostate, pelvic radiation, urethral stricture, or prior surgery for bladder neck obstruction.
- 15. Active urinary tract disease or has undergone cystoscopy or biopsy of the prostate within one month prior to the first screening visit or has an imminent need for urologic surgery.
- 16. Known primary neurologic conditions such as multiple sclerosis or Parkinson's disease or other neurological diseases known to affect bladder function.
- 17. Documented bacterial prostatitis within the past year.
- 18. Two documented independent urinary tract infections of any type in the past year.
- 19. Known severe bleeding disorder or need for ongoing therapeutic anticoagulation with Coumadin, Heparin, or Plavix.

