#### 3.3 Randomization and Stratification

Following a successful screening period, the participant will be officially randomized to one of the two treatment groups:

- Serenoa Repens
- Placebo

This study will use a stratified randomization scheme with equal numbers of participants in each treatment group. Stratification will be by clinical center and AUA Symptom Score (8-15; 16-24). Within each stratum, the method of randomly permuted blocks will be used to ensure that an equal number of participants are assigned to each treatment group.

Clinical Centers will randomize participants to treatment groups using a centralized, data-based system. Password protection will be implemented to ensure that only certified clinical center personnel are allowed to randomize patients. At the time of randomization, each participant will be assigned a unique medication kit identification number that will be used throughout the duration of the study.

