#### 8.0 STATISTICAL CONSIDERATIONS

#### 8.1 Sample size estimation

The primary goal of this study is to determine the efficacy and safety profile of treatment with *Serenoa Repens* compared to placebo. The primary end point of the study is change in AUA symptom score from baseline to 72 weeks. The sample size estimate is based on the following assumptions: a difference in the change in the AUA symptom score from baseline to 72 weeks of 2 points between the placebo arm and the phytotherapy arm, a common standard deviation of the AUA symptom score of 6 points, a two-group t- test, a one-sided significance level of 0.05 and a statistical power of 90%. A one-sided statistical test will be used since an improvement in the AUA symptom score with therapy (i.e., efficacy of therapy) is of primary interest. To detect the hypothesized difference in the change in the AUA symptom score, a sample size of 157 participants per arm will be required. Therefore, a total of 314 participants will be required for the study. To allow for a 10% dropout rate over the course of the study, 350 participants will be recruited to the study.

To determine the power for evaluating safety by measuring hematology and serum chemistry levels, it is assumed that the underlying probability of a severe or life-threatening adverse event detected by laboratory results for placebo is < 2.5%. With 157 participants in each treatment arm, the power to detect a severe or life-threatening adverse event that occurs with frequency  $\ge 10\%$  in the phytotherapy arm at the one-sided 0.05 significance level is 80%.

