#### 8.2.5 Subgroup Analysis

It is anticipated that the primary and secondary outcomes will be evaluated for racial/ethnic groups. Differences between the phytotherapy and placebo arms will be examined separately for each racial/ethnic group.

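### Baseline measures are analysed for subgroup effects only as sample thirds or a two-way split, which discards about 15% to 20% (thirds) or 35% to 50% (NIH-CPSI) of the information on effect modification if modification is roughly linear

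*Combined protocol and SAP*

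**What the plan says.** Section 2.3 (Subgroups) lists AUA Symptom Index and BPH Impact Index together as one item, then peak uroflow, post-void residual, PSA and the NIH-CPSI. For all but the last, "three ordered categories will be created based on textiles of the respective distributions, and the relationship of the ordered categories to the outcome variables" is to be studied (I read the odd word as tertiles). For the NIH-CPSI, "the score will be dichotomized into two ordered categories, the threshold considered to indicate significant symptoms of chronic prostatitis"; no numerical cut point follows.

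Section 8.2.5, the subgroup section of the analysis plan, deals only with race and ethnicity: "Differences between the phytotherapy and placebo arms will be examined separately for each racial/ethnic group". It does not mention the baseline measures. Neither section names a model, an interaction test or an analysis on the original scale. Sections 4.1 and 4.2 and Appendix I show that all six measures are collected at screening or baseline as continuous values or multi-level scores, so the full-scale data will exist.

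**The concern.** These analyses are there to show whether the effect of treatment varies with baseline severity, flow, residual volume, PSA or prostatitis symptoms. Cutting the measure treats a man at the edge of a third like one in its middle, and separates two nearly identical men on either side of a cut. When the effect changes gradually with the baseline value, this throws away information.

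The cut points for the thirds also depend on who happens to enrol, so they cannot be stated in advance and will not carry over directly to another trial. The documents give no clinical reason for them.

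The trial is sized for one overall comparison, and no power is stated for any subgroup question. These analyses are therefore already weak, and a further avoidable loss makes an uninformative answer more likely.

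**Working it through.** **Inputs from the documents.** Section 8.1: a 2-point difference ("a difference in the change in the AUA symptom score from baseline to 72 weeks of 2 points"), SD 6, one-sided 0.05, 90% power, 157 per arm, 314 in total, 350 with 10% dropout. Section 3.3: equal allocation, and the AUA range ("Stratification will be by clinical center and AUA Symptom Score (8-15; 16-24").

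**Assumptions, not in the documents.** The shape of each baseline distribution, linear effect modification, the size of that modification, a two-sided 0.05 interaction test, and the share of men above the NIH-CPSI threshold.

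**Step 1: the plan's own figure.** n per arm = 2 × (1.645 + 1.282)² × 6² / 2² = 154.2, so 155. The stated 157 gives 90.4% power by the noncentral t. 314 / 0.9 = 348.9, so 349 against the stated 350. The stated size reproduces closely, and I use 157 per arm below.

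**Step 2: information kept.** For linear modification, the share kept is the squared correlation between the measure and its category score.

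- Thirds of a normal measure, scored -1, 0, 1: (2 × φ(0.4307))² / (2/3) = (2 × 0.3636)² / 0.6667 = 0.793. Loss 21%.
- Two groups, normal measure, share q below the cut: φ(z_q)² / (q(1 - q)). For 50/50: 0.3989² / 0.25 = 0.637, loss 36%. For 80/20: 0.2800² / 0.16 = 0.490, loss 51%.
- AUA score, whole numbers limited to 8-24, assumed mean 15 and SD 4.5 or 6 before truncation: loss 13% to 17%, depending on the SD and on how ties at the cut are placed.

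Out of 314 men, the information left equals that from about 249 (314 × 0.793), 200 (314 × 0.637) or 154 (314 × 0.490).

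**Step 3: what this does to power.** The standard error of the interaction slope per baseline SD is 6 × √(2/157) = 0.677. Approximate power is Φ(slope / 0.677 × √(share kept) - 1.96), plus a negligible opposite tail.

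| Change in effect per baseline SD | Full scale | Scored thirds (0.793 kept) | Loss, points |
|---|---|---|---|
| 2.0 | 84% | 75% | 9 |
| 1.5 | 60% | 50% | 10 |
| 1.0 | 31% | 26% | 5 |
| 0.75 | 20% | 17% | 3 |
| 0.5 | 11% | 10% | 1 |

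Losses are computed before rounding. Simulating the two largest slopes gives 82% against 72% at 2.0 and 60% against 50% at 1.5.

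For a two-group split, simulated power at 2.0 points per SD is 62% (50/50) and 52% (80/20). At 1.5 it is 41% and 34%.

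**Step 4: other shapes.** Thirds of a uniform measure lose 11%. A skewed measure loses more if the effect is linear on the raw scale: 31% for a gamma with shape 2, and 35%, 46% and 65% for lognormals with log-SD 0.5, 0.7 and 1.0. If the effect is linear on the log scale, a lognormal measure loses 21%. The documents do not give the distributions of PSA or post-void residual. PSA is at least bounded above by an exclusion ("PSA level greater than 10 ng/ml at the first screening visit").

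**The case against.** **The loss depends on a strong gradient.** With an average effect of 2 points, a slope of 2 per SD implies no effect at -1 SD, 2 points of harm at -2 SD and 6 points of benefit at +2 SD. At 1.5 per SD the effect still changes sign, at -1.33 SD. Nothing in the documents suggests modification that large. At 1.0 and below, power is poor on either scale, and the full scale does not rescue the analysis. This stands, and it limits the practical gain.

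**The plan names no interaction test.** Section 2.3 promises only to examine a relationship, so the power figures describe a test that a reader has to supply. That is fair. Whatever comparison is used, though, it will be made on the cut variable, and naming the model is part of the fix.

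**The NIH-CPSI cut has a reason.** It is tied to significant symptoms of chronic prostatitis. If the effect steps there, dichotomising loses little or nothing. This stands. The missing value is a gap in specification, separate from loss of information.

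**Thirds have merits.** They are defined by rank on baseline data, not on outcomes, and need no linearity assumption. A reader should therefore not infer that the cut points could be picked to suit the result.

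**Stronger readings to avoid.** A reader might infer that every measure loses 20% to 50%, or that power falls by 10 to 30 points whatever the truth. The first merges two cases: the upper part of that range belongs to the NIH-CPSI split under a normal model, and the AUA score falls below its lower end. The second fails at 1.0 point per SD and below. It also leans on treating the thirds as unordered, whereas the plan calls them ordered.

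**Conclusion.** The concern holds as a modest loss of efficiency in the subgroup analyses. For a near-normal measure with roughly linear modification, thirds discard about 20% of the information (about 15% for the AUA score). The NIH-CPSI split discards about 35% to 50% for splits between 50/50 and 80/20; the actual share is unknown. Scored thirds cost from about 1 to about 10 power points as the gradient rises from 0.5 to 2 points per SD. Strong skew on the raw scale would make the loss larger, and a step near a cut point would make it small or absent.

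The primary comparison, its sample size and the secondary longitudinal analyses are untouched. This is a worthwhile improvement to the plan; it does not threaten the trial's main conclusion.

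**What to change.** In sections 2.3 and 8.2.5:

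- State that effect modification by each of the six measures will be assessed mainly through a treatment-by-baseline interaction with the measure on its full scale. Use a log scale for PSA and post-void residual if they are skewed, with a small constant added where zeros occur.
- Report the fitted treatment difference with its confidence interval across the observed range of the measure.
- Add a quadratic or restricted cubic spline term as a check on linearity.
- Keep the thirds and the NIH-CPSI threshold for descriptive tables, and write down the threshold value.

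The cost is a few lines of text and one or two model terms per measure. No new data or participants are needed. The downside is that the main assessment assumes a linear trend, which the quadratic or spline check covers.
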